Thus, CSA represents an effective therapy for inducing remission of nephrotic syndrome in patients with IMN. It leads to remission of proteinuria in the majority of nephrotic patients with IMN but with less potential serious toxicity compared to the use of cytotoxic/alkylating agents. There is also more experience with CSA (versus other CNI) in the US and Canada and for these reasons it has been chosen as the comparator arm for our study.

Patients with IMN that do progress do so over years and follow-up in RCTs with CNI therapy have not been of sufficient duration to illustrate improvements in renal survival. However there is well documented recent data that indicates that both complete and partial remission in proteinuria is associated with improved renal survival. Complete remission was associated with a 100% 10-year survival and partial remission (defined as more than a 50% decrease from baseline and attaining a urine protein level of <3.5 g per day) was associated with a 90% 10 year renal survival compared to 50% kidney survival in those that fail to remit. In addition, in this same study PR as measured by slope of CCR, resulted in a slowing of progression rate of >80 % compared to non-remitters.⁴²

Toxicity of cyclosporine

Cyclosporine is a potent immunosuppressive agent and is associated with significant risk of both short and long-term toxicity. In the majority of cases these adverse effects are associated with both total daily dose and total exposure. Precise incidences of these toxicities are hard to ascertain from the literature given the rarity of studies where these agents are used as monotherapy and their use for a limited duration as proposed in this trial. There is however undoubtedly an acute effect on filtration function and delayed effects on renal vasculature that have been well documented and a recent review summarized both short and long-term toxicities associated with this agent.⁵⁸ Hypertension, overgrowth of body hair and gingiva hyperplasia, mild tremor, infections, elevated bilirubin levels and mild nausea represent the most frequently observed short-term adverse effects related to CSA.⁵⁸ These are seen in up to 20 to 30% of the treated population but are usually tolerated and/or treatable with additional agents (such as additional anti-hypertension drugs) or by dose reduction.⁴⁸

Cyclophosphamide (CYC)

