The goal of this proposal is to conduct a prospective randomized controlled phase III study comparing Rituximab (RTX) to Cyclosporine (CSA) in the treatment of patients with IMN. Once a patient with IMN and proteinuria $\geq 5\text{g}/24\text{h}$ is identified, meets other entry criteria and consents to the study, he/she will receive a minimum of 3 months of conservative therapy aimed at maximizing Angiotensin II blockade (run-in phase). If at the end of this period the patient still meets entry criteria he/she will be randomized into a 12-month treatment period, and a subsequent follow-up of 12 months. Efficacy of treatment will be assessed by remission status (based on changes in proteinuria) at 24 months from randomization. Patient safety will be assessed via collection of adverse event data and evaluation of pre- and post-treatment laboratory data. At the 6-month post-randomization visit, patients who have been randomized to either CSA or RTX but who do not have a reduction in proteinuria $\geq 25\%$ (confirmed on repeat measurements within 2 weeks) will be considered treatment failures and exit the study. Data from that point onward will be censored. Patients in the RTX group who have a reduction in proteinuria of equal to or $>25\%$ at 6 months will be given another identical course of RTX (1g x 2). This treatment regimen was chosen given our initial data that suggested a percentage of our cohort appeared to respond to an additional course of therapy. Data from our 2 pilot studies showed that RTX is out of the circulation by month 2 in the majority of patients and B cells have recovered by month 3 in patients treated with RTX 1g x 2 (the regimen chosen for the study). Thus, at 6 months, patients in the RTX arm are completely, at least as best as we can measure, free of immunosuppression, and hence the second course should not be associated with additive toxicity. The same definition of response will apply to the CSA arm at 6 months. An equal to or $>25\%$ reduction in proteinuria will dictate continuation of the CSA for an additional 6 months (total of 12 months of full dose CSA). This assessment at six months allows a balance between risk-benefit in both arms. The protocol provides similar exposure to immunosuppression in both arms and allows an early exit for patients related to safety issues by providing a lack of efficacy (futility) end point at 6 months.

Primary endpoint

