Rituximab: Patients randomized to the RTX arm will receive 1000 mg IV on Days 1 and 15. Patients who achieve complete remission at 6 months will not be retreated. A second course of RTX 1000 mg IV will be administered at study month 6 for individuals who have not achieved a complete remission, but have achieved at least a $\geq 25\%$ reduction compared to their central laboratory (Mayo Clinic Rochester) baseline (Time 0) proteinuria (but not a CR). Dosing at study month 6 will be independent of CD19/20+ B cell count. The rationale for retreating patients who have had an equal to or $> 25\%$ reduction in proteinuria at 6 months is based on our experience in our pilot studies (first study using 1000 mg on Days 1 and 15 and second study using 4 weekly doses of $375\text{mg}/\text{m}^2$) where an increase in the proteinuria remission rate was achieved after a second course of treatment. In our 2 studies repeated courses of RTX were not associated with additive adverse effects in comparison to their first course. If after six months the reduction in proteinuria is less than 25% compared to baseline the RTX treatment will not be repeated, the patient will exit from the study and will be considered a failure of therapy.

Dosage and Administration of Rituximab: The first infusion of both courses (Day 1 and Day 181) of RTX will be administered IV at an initial rate of 50 mg/hr. All patients

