CSA was 175 ng/ml the goal would be to reduce it to 130 ng/ml by reducing the dose by approximately 25% - dose reduction is approximate because CSA is only available in specific dose strengths (25mg, 100mg) and therefore some rounding may be required). If with this dose reduction the creatinine does not return to within 30% of baseline levels within 3 weeks, then a second dose reduction of approximately 25% with a similar reduction in CSA trough level (e.g. if CSA trough level was 100 ng/ml, reduce to 75 ng/ml) will be used. If the creatinine does not fall to within 30% of baseline values with this second dose reduction, the drug will be discontinued. If after six months the reduction in proteinuria is less than 25% compared to baseline the drug will be discontinued, the patient will exit from the study and be considered a failure of therapy. At the end of 12 months, Cyclosporine will be tapered by 1/3 of the maintenance dose monthly and hence discontinued after 2 months. Serum potassium and serum creatinine levels will be checked at the initiation of Cyclosporine in conjunction with blood draw for CSA level. If Cyclosporine dose is changed during treatment, potassium, creatinine and CSA levels will be rechecked every two weeks +/- 3 days post increase/decrease in CSA dosage until levels are stable and at target.

[figure not shown]

Figure 4. Schematic representation of the study design.

Blinding

This will be an open-label study with neither patients nor physicians blinded. Blinding, for this study, was considered difficult and unnecessary and would significantly add to the cost of the study. The need to provide RTX intravenously would require that the CSA arm patients would have to receive an IV infusion of saline which seems unjustifiable from the scientific and budgetary points of view. Furthermore, with the exception of

quality of life measures, all endpoints are based on objective (laboratory) criteria. Having the physicians in the study blinded to CSA level also introduces a potential risk factor that's unnecessary in our estimation. Documentation of cyclosporine levels will ensure that patients are taking the drug at the appropriate time and achieving the prescribed levels indicated in the protocol.

Pharmaceutical logistics

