Candidates who have already been on conservative therapy for 3 months or more without a documented decrease in proteinuria of >50% as compared to a value from within the last 3 to 12 months do not need to fulfill the run-in requirement as long as their local labs indicate that proteinuria remains $\geq 5\text{g}/24\text{h}$. These individuals should proceed directly to full screening as part of the Time 0 visit and do not require a formal screening visit. Review of the eligibility criteria, lab requirements, and the review and signing of the informed consent form will take place at the Time 0 visit for these individuals. However, retrospective data from at least two previous time points (approximately 3 months prior to obtaining consent plus one more time point within the previous year) will still be collected whenever possible. Retrospective data collection needs to include proteinuria, urine creatinine, creatinine clearance, Uprot/Ucrea ratio, systolic blood pressure, diastolic blood pressure, serum creatinine, and serum albumin values.

Patient monitoring and evaluation

Patients will be followed for 2 years following randomization to monitor for the occurrence of adverse events, late remissions, relapses, GFR changes and development of

end stage renal disease. The first 12 months of the study will be considered as the treatment period while the remaining 12 months will be considered as an observational period including the period of tapering to discontinuation in the Cyclosporine arm. In addition, as described later in the protocol (see ancillary studies) we will seek permission to follow the remission cohort (i.e., those in PR or CR at 12 months or CR at 6 months as well as those who are not in remission but have a $\geq 50\%$ reduction in proteinuria from baseline by month 12) for an additional 12 months of observation beyond the previous end point of observation of 24 months to monitor for relapses and changes in PLA2R.

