For those patients in the Cyclosporine arm, **Cyclosporine trough level measurements will be done every 2 weeks +/- 3 days after initiation of Cyclosporine until levels are stable and at target. Potassium and creatinine will also be checked in conjunction with CSA level. If Cyclosporine dose is changed during treatment, potassium, creatinine and CSA level will be rechecked every 2 weeks +/- 3 days until levels are stable and at target.** Cyclosporine levels will also be assessed whenever serum creatinine rises by $>30\%$ without a recognizable reason such as volume depletion, additional drugs, sepsis, etc. Patients who cannot tolerate the medications and/or who are treatment failures at 6 months will exit the study at 6 months (i.e., the 6 month visit and accompanying data collection should still occur). Patients who go in to complete remission will discontinue study drug but will continue with full visit follow-ups until month 24 as scheduled. However, the therapeutic/management plan for these patients will be solely at the discretion of the managing nephrologist although while in CR no further immunosuppressive therapy is recommended. Likewise, patients who relapse from either a partial or complete remission or who are not in partial or complete remission by the end of the treatment period (i.e., 12 months) will continue with the visit schedule, but the therapeutic/management plan will be solely at the discretion of the managing nephrologist. Finally, for patients who temporarily stop taking Cyclosporine, there are three possible scenarios:

1. Patients who discontinue Cyclosporine for < 2 weeks may simply be restarted on the study drug and continue to fully participate in the trial. The treatment is to be restarted at its former dose and the patient returned to the regularly scheduled follow-ups including the periodic sampling for assessing potassium, creatinine and CSA trough levels.
2. Patients who discontinue Cyclosporine for ≥ 2 weeks, but < 4 weeks may also be restarted on the study drug at its former dose and fully participate in the trial, but the temporary discontinuance will be logged as a protocol deviation and the missed treatment days will be made up at the end of month 12. This is to ensure that all patients receive approximately 12 months of treatment with study drug.

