After the second course of RTX therapy at six months they will have no further RTX therapy regardless of their proteinuria level
3. Significant potential life threatening infection.
4. Persistent elevation of liver enzymes >2 x normal (despite CSA arm dose reduction).
5. Persistent elevation of serum potassium >6.0 mEq/l despite diet changes, ACEi/ARB reduction, diuretic dose increase (and in the CSA arm dose reduction).
6. A rise in serum creatinine by $>30\%$ above baseline that persists in the absence of secondary causes such as volume depletion or use of potential nephrotoxic agents (and despite adjustments in the CSA dose)
7. Persistent hypertension in either arm, i.e. supine blood pressure >160 mmHg systolic or >90 mmHg diastolic, despite institution of maximum antihypertensive therapy (and despite adjustments of CSA dose)

8. Other clinically relevant adverse effects not resolved by reduction in dosage of test medications.
9. Development of any malignancy or lymphoproliferative disorder.
10. Pregnancy.
11. The appearance of an independent disease whose standard therapy requires continuous administration of significant amounts of corticosteroids, other immunosuppressive agents or plasma exchange therapy.
12. Serious concomitant disease with an expected survival of less than 4 years.
13. At the wish of the patient.
14. The study will be placed on hold if 3 of the first 5 patients enrolled and treated with RTX or CSA develop severe opportunistic infections, or experience Grade 3-4 SAEs.

Patients who choose to discontinue study medication or are withdrawn because of adverse events will be strongly encouraged to continue follow up examination to the study termination.

Ancillary studies:

1. DNA Testing

Recent data show that in patients with membranous nephropathy, mutations in HLA-DQA1 and PLA2R1 alleles are associated with an increased risk for developing membranous nephropathy.⁸⁰ One of these alleles, the PLA2R1, is in fact the gene for the PLA2 receptor. In our pilot studies, ~70% of the patients with membranous nephropathy had antibodies present in circulation against PLA2 receptor.⁷⁷ Thus we would like to evaluate a linkage between the presence of these antibodies and potential genetic mutations in this group of patients. We will ask for the patients consent to further evaluate this linkage by collecting samples of blood to perform additional testing as part of their informed consent form (ICF).

2. Quantitative gene expression analysis

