related) of the serious adverse event. The medical monitor [and, if applicable, sponsor] may request further information if necessary and possibly request changes to the protocol or consent form as a consequence of the serious adverse event. A back-up notification system is in place so that any delays in review by the medical monitor beyond a specified period of time are forwarded to a secondary reviewer. The eCRF maintains audit trails and stores data (and data updated) related to any adverse event in the study.

Study Discontinuation

The Study Sponsor, DSMB and local IRBs (at their local site) have the authority to stop or suspend this trial at any time. This study may be suspended or closed if:

- Accrual has been met
- The study objectives have been met
- The Study Investigators believe it is not safe for the study to continue
- The DSMB suspends or closes the trial

Subject Discontinuation

An intent to treat approach will be used. All data acquired prior to termination for the reasons outlined below will be included in the primary analysis unless patient withdraws consent. Every effort will be made to conduct a final study visit with the participant and participants will be followed clinically until, if applicable, all adverse events resolve.

Reasons for subject discontinuation include:

- Withdrawal of consent
- Withdrawal by the participant
- Withdrawal by the investigator
- Intercurrent illness or event that precludes further visits to the study site

Regulatory issues:

1. Inclusion of women: Women make up approximately 30-50% of the population of patients with IMN and are expected to be enrolled in numbers in proportion to this normal distribution.
2. Inclusion of minorities: Individuals of all races and ethnicities are at risk for MN. Based on the ethnic composition of the patients followed at, and referred to the Mayo Clinic the population served will include African-Americans, Asian, and Hispanic subjects proportional to that in the general US and Canadian population. This will ensure adequate enrollment within the different racial groups.

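### Patients who leave for non-response at month 6 have no ESRD follow-up afterwards, although ESRD is a secondary endpoint and the protocol promises 2 years of follow-up for it

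*Combined protocol and SAP*

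**What the plan says.** The section on patient monitoring and evaluation sets the general rule: "Patients will be followed for 2 years following randomization to monitor for the occurrence of adverse events, late remissions, relapses, GFR changes", with ESRD named at the end of the same sentence. The list of secondary endpoints includes ESRD as item 5, without a definition, a time point or a rule for missing data.

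Four places set a month-6 exit for patients with less than a 25% reduction in proteinuria:

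- Overall research design: these patients "will be considered treatment failures and exit the study. Data from that point onward will be censored".
- Rituximab arm: "the patient will exit from the study and will be considered a failure of therapy".
- Cyclosporine arm: "the drug will be discontinued, the patient will exit from the study and be considered a failure of therapy".
- Patient monitoring and evaluation, shortly after the 2-year promise: "Patients who cannot tolerate the medications and/or who are treatment failures at 6 months will exit the study at 6 months".

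The statistical section counts a patient with neither a 24-month nor an 18-month result as a failure, but only for the primary proteinuria endpoint. It censors renal function readings at dialysis or transplant. It specifies no ESRD analysis and does not say how ESRD is scored in a patient who has exited.

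**The concern.** For a month-6 non-responder, 2 years of follow-up for ESRD and exit with censoring cannot both apply. After exit, ESRD status is unknown. Scoring it as absent has no support, and dropping the patient departs from analysis of all randomised patients.

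The loss is not random with respect to the outcome. Exit is decided by proteinuria response, and the background on cyclosporine ties remission to kidney survival: complete remission went with 100% 10-year renal survival, while partial remission "was associated with a 90% 10 year renal survival compared to 50% kidney survival in those that fail to remit". Censoring on non-response is therefore likely to be informative for ESRD. If one arm has more exits, more of its later events go unseen, and it would look better on ESRD than it is. Late remissions and renal function after exit are lost in the same way.

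**Working it through.** **1. Who leaves and who stays.** The exit applies to month-6 non-responders and to patients who cannot tolerate study drug. The monitoring section keeps the following on visits to month 24: patients in complete remission, relapsers, patients not in remission at month 12, and patients off cyclosporine for 4 weeks or more. On the planning rates (45% cyclosporine, 55% rituximab, 63 per arm), month-24 non-remitters number 63 × 0.55 + 63 × 0.45 = 63. With 13 to 32 exits (step 3), about 31 to 50 of them would remain on schedule, less any lost for other reasons.

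**2. The plan's own figure.** The only relevant stated figure is the primary sample size. With a 15-point margin and one-sided alpha 0.025:

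n = (1.960 + 0.842)² × (0.45 × 0.55 + 0.55 × 0.45) / (0.10 + 0.15)² = 62.16, so 63 per arm, with 80.5% power at 63.

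This reproduces the plan. Month-6 failures already count as primary failures, so following them for ESRD leaves it unchanged.

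**3. Follow-up time lost.** The exit share is not stated. Someone with less than a 25% reduction cannot meet either remission definition, so exits are a subset of patients not in remission at month 6. The sample-size section gives 60 to 75% remission on cyclosporine, hence 25 to 40% without. There is no month-6 figure for rituximab. I assume 10 to 25% overall. Each exit loses 18 of 24 months, out of 126 × 2 = 252 planned patient-years.

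- 10%: 12.6 patients × 1.5 years = 18.9 patient-years (7.5%).
- 25%: 31.5 patients × 1.5 years = 47.25 patient-years (about 19%).

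**4. Events missed (illustration).** Spread the 50% 10-year kidney survival of non-remitters evenly over time: hazard = −ln(0.5)/10 = 0.0693 per year. The probability of ESRD between month 6 and month 24 is

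exp(−0.0693 × 0.5) − exp(−0.0693 × 2) = 0.9659 − 0.8706 = 0.0954 per patient.

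- 10% exits: 12.6 × 0.0954 = 1.2 events.
- 25% exits: 31.5 × 0.0954 = 3.0 events.

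I give no share of all ESRD events. That share depends almost entirely on the hazard assumed for the patients who stay, which the documents do not settle.

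**5. Difference between arms.** If exit shares differed by 10 points, that is 6.3 patients, the difference in missed events would be 6.3 × 0.0954 = 0.6. If the shares were equal, there would be no differential loss under this model.

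**The case against.** The strongest reply is that this is a general rule with a stated exception. The exit appears in the same section as the 2-year promise and is repeated elsewhere, and the design section justifies it as an early exit on safety grounds through a lack-of-efficacy endpoint. That reading is fair, but it does not say how ESRD is handled after exit. The safety reason concerns exposure to treatment, not collection of outcomes.

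Other text may seem to fill the gap. Under the stopping points, "Patients who choose to discontinue study medication or are withdrawn because of adverse events will be strongly encouraged to continue follow up examination", but this covers patient choice and adverse-event withdrawal, not non-response. It also sits awkwardly with the rule that intolerant patients exit. Under subject discontinuation, a final visit is sought and "participants will be followed clinically until, if applicable, all adverse events resolve", which is not ESRD ascertainment to month 24. Adverse events are to be reported up to study termination, but the text does not say whether that means the patient's exit or the end of the trial.

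The objections on size largely stand. Entry requires estimated GFR or creatinine clearance of at least 40. The inclusion criteria call the chance of detecting a significant GFR change in this short study remote, and the background describes slow progression over years. A constant hazard from randomisation therefore probably overstates early events. Proteinuria can also fall gradually after rituximab, so some month-6 non-responders might remit later and not carry the full non-remitter hazard. Finally, the sample-size section expects similar initial remission rates in the two arms and more relapse after cyclosporine, and relapsers are retained.

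A reader might infer that ESRD cannot be scored at all in the patients most likely to reach it. The documents do not support that: everyone is observed to month 6, and many non-remitters and all relapsers on schedule are observed to month 24.

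**Conclusion.** The gap is real but limited. ESRD after month 6 goes unrecorded in patients who exit for non-response, and no passage supplies a rule for them. The loss is selective because exit depends on response. Bias between arms follows only if exit shares differ, so a reader should not infer that the ESRD comparison is already biased in a known direction.

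The size is small in absolute terms: about 1 to 3 missed events as an upper-end illustration, resting on an assumed 10 to 25% exit share and a constant non-remitter hazard. When few events are expected, even one or two lost selectively can matter to how the endpoint reads, but the trial is not powered for ESRD and no test of it is specified. The primary endpoint remains scorable, and the sample size stands. This is a cheap improvement affecting a secondary endpoint only.

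**What to change.** Reconcile the month-6 exit text in the overall design, both treatment-arm descriptions and the monitoring section with the 2-year follow-up statement, so that leaving protocol treatment and efficacy visits is distinct from leaving outcome follow-up. In the same edit, reconcile the data-collection rules for patients who cannot tolerate study drug. The treatment rules themselves need not change.

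Then:

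- Record dialysis, transplant and death to month 24 for every randomised patient, including month-6 failures, by chart review or telephone.
- Define ESRD, and state that it is analysed in all randomised patients to month 24.
- Leave primary endpoint scoring and the 63 per arm as they are.

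The cost is a short protocol and consent amendment and one chart check or call per exited patient, about 13 to 32 on the assumed exit share, with no added tests or clinic visits. The protocol already accepts off-treatment follow-up to month 24 for relapsers, month-12 non-remitters and patients off cyclosporine for 4 weeks or more. Outcomes that are not collected cannot be recovered by analysis later.
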